2. Evaluate the impact of My Diabetes GOAL vs. My Diabetes GOAL + CRx vs. Attention control on self-care:

- a. Diabetes self-efficacy and self-management behaviors (e.g., physical activity);
- b. Knowledge and utilization of community-based resources.

3. Evaluate the impact of My Diabetes GOAL vs. My Diabetes GOAL + CRx vs. Attention control on clinical outcomes and health care utilization:

- a. Glycemic control and hypoglycemia;
- b. Geriatric syndrome symptom burden (e.g. depression, falls, incontinence);
- c. Functional status;
- d. ED visits and unplanned hospitalizations.

Personalizing diabetes care in older African American patients with strategies that acknowledge personal preference, barriers to self-care and community connections have the potential to improve the overall quality of life while minimizing adverse drug events like hypoglycemia. The likelihood of sustainability and replicability of My Diabetes GOAL and CRx are high because both can be delivered remotely, and both leverage existing clinical staff, electronic health record systems, and community resources.¹⁷

C. Methodology

Potential study subjects will be identified and pre-screened through the electronic medical record of the University of Chicago. Physician assent will be obtained to approach a patient. Then a research assistant will approach the potential participant to explain the purpose, intervention and potential benefits/risks of participating in this study. All human subjects will be consecutively screened for inclusion and enrolled as described in Section P. Recruiting Methods. A research assistant will conduct informed consent with eligible subjects prior to any study procedures.

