Aims 2 and 3: To compare self-care continuous outcomes and clinical continuous outcomes including A1C (primary outcome) over the three study groups, a repeated measure analysis of variance via LMM will be performed to model one outcome over time and test the effects of treatment, time and their interaction. Clinic will be considered as random effects in a LMM to account for within-site association. We will fit an unadjusted model first and then an adjusted model adjusting for baseline outcome and participant-level potential confounders as mentioned above. Normality will be checked and appropriate data transformation will be performed if data highly skewed. The p-value for the group comparison between MDG and MDG+CRx in A1C at 12 months will be used for the primary objective analysis at the two-sided significance level of 5% (consistent to the power justification (below)). Multiple pairwise comparisons will be conducted to compare between groups at each time point and compare the multiple time points within a group. All the multiple comparisons and analyses of all the secondary outcomes will be considered to be exploratory and will not spend the overall type I error rate of 5%. To compare each of binary outcomes such as utilization of community-based resources, we will use GEE and GLMM for group comparisons, as mentioned in analyses of Aim 1. To compare health care use (ED and hospitalizations), we will use both Poisson and negative binomial regression models. If the health care use data are zero-inflated (i.e., >50% of patients who have no service use), we will use both zero-inflated Poisson and zero-inflated negative binomial models.

Sensitivity analyses: We will also assess the impact of our interventions across patient subgroups (age group, health status, baseline A1C group, and diabetes duration with different thresholds).

Interim analyses: We will apply the statistical methods above to all the available data including baseline, all 6-month follow-up data, and about 75% 12-month follow-up data.

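### The 50% cut-off for zero inflation in ED visits and hospitalizations measures the share of zeros rather than an excess of zeros, and no main count model is named (minor; exploratory outcomes)

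*Combined protocol and SAP*

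**What the plan says.** The rule is in Section I (Statistical analysis), in the paragraph on Aims 2 and 3. The default is stated first: "To compare health care use (ED and hospitalizations), we will use both Poisson and negative binomial regression models". The condition follows: "If the health care use data are zero-inflated (i.e., >50% of patients who have no service use), we will use both zero-inflated Poisson", and the sentence goes on to name the zero-inflated negative binomial as well.

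The same paragraph plans between-arm contrasts: "Multiple pairwise comparisons will be conducted to compare between groups at each time point". It sets the status of these outcomes: "All the multiple comparisons and analyses of all the secondary outcomes will be considered to be exploratory". The confirmatory test lies elsewhere: "The p-value for the group comparison between MDG and MDG+CRx in A1C at 12 months will be used for the primary objective analysis". The outcome itself is Aim 3d in Section B, "ED visits and unplanned hospitalizations", and it appears again in Table 1.

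For these count models the documents give no expected event rate, dispersion, variance estimator or fit criterion. They do not say which model in a pair supplies the reported result, or which part of a zero-inflated model contains study arm.

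**The concern.** Zero inflation means more zeros than the count distribution would itself produce. The plan's definition compares the observed zeros with no such expectation. A rare event, or an overdispersed one, passes 50% zeros with no separate class of never-users. The rule can therefore bring in zero-inflated models for a feature that is absent.

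The second gap is that each branch names two models and ranks neither. With three arms, each outcome has three pairwise contrasts. If the two fits differ on a contrast, the plan does not say which one carries the conclusion.

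At stake is how the ED and hospitalization results are read: a report could describe a never-user class that does not exist, or quote whichever of two fits reads better.

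**Working it through.** **Inputs from the documents.** 505 randomized patients (Sections B and H) and 1:1:1 allocation (Section C), so 505/3 ≈ 168 per arm; the cut-off of more than 50% zeros (Section I). The plan gives no figure to reproduce for these outcomes.

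**Assumptions.** All means, NB sizes k (variance = m + m²/k) and standard-error choices below are assumed and shown as a range.

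**Step 1. Mean at which half the patients have a zero, with no excess zeros.**
- Poisson: exp(−m) = 0.5 gives m = ln 2 = 0.693.
- NB: (1 + m/k)^(−k) = 0.5 gives m = k(2^(1/k) − 1), which is 1.0 for k = 1 and 1.5 for k = 0.5.

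Any lower mean gives an expected share of zeros above 50%.

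**Step 2. Chance that the rule fires with 505 patients and no excess zeros.** More than 50% means at least 253 patients, so the chance is P(Binomial(505, P0) ≥ 253).

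| Counts | Mean: chance of firing |
|---|---|
| Poisson | 0.5: >99.9%; 0.69: 53%; 0.8: 1% |
| NB, k = 1 | 0.8: 99%; 1.0: 50%; 1.2: 2% |
| NB, k = 0.5 | 1.0: >99.9%; 1.5: 50%; 2.0: 1% |

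**Step 3. What ZIP then estimates.** Take two NB settings with no never-users: A (mean 0.5, k = 1; 66.7% zeros) and B (mean 1.0, k = 0.5; 57.7% zeros). The rule fires almost surely at both. Over simulated data sets the average ZIP never-user share is 42% at A and 51% at B. Fitting ZIP by maximum likelihood to the exact NB distributions gives 43% and 52%.

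**Step 4. Null rejection at nominal 5%** (two arms of 168, unadjusted; arm in the count part only for ZIP and ZINB).

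| Fit | A | B |
|---|---|---|
| ZIP, likelihood-ratio test | about 6–8% | about 19% |
| ZIP, sandwich errors | 4.4–5.0% | 5.4–6.9% |
| ZINB, likelihood-ratio test | 5.2% | 5.7% |
| Poisson, model-based errors | 10.6% | 24.4% |
| Poisson, robust errors | 4.8% | 5.1% |
| NB | 4.8% | 4.9% |

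Closed-form check for model-based Poisson: 2Φ(−1.96/√(1 + m/k)). At A this is 2Φ(−1.96/√1.5) = 11.0%; at B it is 2Φ(−1.96/√3) = 25.8%.

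**Step 5. Disagreement on p < 0.05 in null data sets.**
- Poisson against NB: 5.7% (A) and 19.5% (B) with model-based Poisson errors; 0.4% and 0.7% with robust errors.
- ZIP against ZINB: 1.6% (A) and 13.8% (B) with likelihood-ratio tests. In a separate 700-run check at B, sandwich errors for ZIP cut disagreement from 14.9% to 5.9%; at A it was about 2% either way.
- For true Poisson counts with mean 0.5, ZIP and ZINB each rejected 5.0% and never disagreed.

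**Step 6. The opposite error.** With 30% never-users and Poisson mean 3 in the rest, the share of zeros is 0.3 + 0.7·exp(−3) = 33.5%, so the rule does not fire. The best-fitting NB (mean 2.10, k = 1.49) predicts 27.0%. NB null rejection in this case was 2.9%, so the planned NB fit does not over-reject.

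**The case against.** The strongest reply is that the consequence is small and mostly not caused by the cut-off. The 19% for ZIP comes from model-based likelihood-ratio tests, and sandwich errors bring it close to nominal. ZINB, which the plan fits alongside, holds near 5%. On another reading of the conditional sentence, the zero-inflated models are added to the first pair and do not replace it, so the NB fit is reported in every case. Showing two models side by side is defensible for outcomes that the plan labels exploratory and that spend no type I error. Robust Poisson performs as well as NB in these checks, so preferring NB is partly taste.

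Most of this stands and it limits the size of the point. It does not rescue the definition: the share of zeros still says nothing about excess, and the spurious never-user share remains under any variance estimator. Nor does it supply the missing hierarchy, because reporting both fits leaves open which one governs when they differ.

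A reader might infer that the cut-off in itself inflates false positives for ED visits and hospitalizations. The documents do not support that: they state no variance estimator, and the inflation largely depends on assuming model-based tests. A reader might also infer that the rule will misfire in this trial. With no event rates or dispersion in the documents, that cannot be said.

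**Conclusion.** The point holds as a minor one. The 50% rule is a wrong definition whatever the event rate turns out to be, and no governing model is named in either pair. How often the rule misfires depends on assumed rates: from about 1% to almost certain over plausible-looking means, with no excess zeros in any of them. After a misfire on overdispersed counts, the lasting harm is a reported never-user class of 42–51% that does not exist. Excess false positives arise mainly if Poisson or ZIP is used with model-based errors, which the plan neither states nor excludes. True zero inflation that the rule misses does little damage, because NB is fitted anyway.

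The outcomes are secondary and exploratory. It would be wrong to read this as casting doubt on the trial's main result: the 12-month A1C comparison of the two intervention arms uses a different model and is unaffected.

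**What to change.** In Section I, Aims 2 and 3:
- Delete the 50% cut-off.
- Name one main model robust to overdispersion for each count outcome, with its variance estimator, and report its rate ratio for each between-arm contrast. NB with robust standard errors is one choice; Poisson with robust standard errors is an acceptable equivalent.
- Judge excess zeros by comparing the observed number with the number predicted by the fitted NB.
- Keep the remaining fits as supportive. For any zero-inflated fit, state which part contains study arm and report the ratio of overall means.

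The cost is SAP wording and a small added analysis, with no new data. Intervals will be wider than model-based Poisson intervals when counts are overdispersed.

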Usual care for diabetes at the University of Chicago is constantly evolving and has features that are important to describe and acknowledge. Since 2018, [name] has been co-chair for diabetes quality improvement at University of Chicago Medicine. University of Chicago has high rates of poor diabetes control based on the quality measure of A1C>9.0%. To reduce rates of poor control, the ambulatory quality improvement team has: 1) conducted system wide outreach to patients to get an A1C test, 2) installed Best Practice Alerts to remind physicians to order lab tests for diabetes, 3) installed point of care testing to primary care clinics, 4) created new drug prescribing SmartSet modules, and 5) organized and vetted patient education materials. University of Chicago also has diabetes education programs, a specialized pharmacist designated to solve problems with high drug prices. This collection of interventions has been associated with steady decline in the rates of poor control (29.2% in April 2019 to 26.6% in March of 2020).

To reduce the chance that benefits from the My Diabetes GOAL arms are due to attention alone, we will also conduct monthly calls to attention control subjects but will not discuss specific issues related to diabetes care. These calls will also help to ensure retention of attention control subjects in the study.

To reduce bias, we will blind participants to the arm of the intervention at the time of enrollment.

H. Type and number of experimental subjects

Individuals will be contacted for enrollment using methods described below in Section P. Recruiting Methods. Individuals will be contacted, screened for inclusion, recruited for study participation and participate in the informed consent process. We plan to enroll up 517 patients (12 in the pilot, 505 in the RCT). We will determine trial arm assignment through a random number generator. Patients will be blinded to study hypotheses and will be unaware of allocation. Our data analyst will be blinded to the treatment allocation of patients.

Inclusion Criteria:

- Males and females 60 years of age or older
- A1C 7.5% or greater
- Clinical encounter at UChicago practice in prior year
- Have access to a cell phone and provides the research interviewer with the cell phone number with internet access OR have a personal email address.

Exclusion Criteria:

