Qualitative interview data will be systematically collected and analyzed using rapid qualitative methods.¹¹⁷ Rapid qualitative methods are well-suited for mixed methods studies and commonly used in implementation science studies when quick understanding of qualitative data is needed to inform next steps or to help interpret or triangulate findings. Rapid qualitative methods use constant comparison of data to inform continued data collection, and analysis is conducted during data collection through the use of text summaries.

Focus groups will be audio-recorded to ensure the accuracy of participants' responses. Researchers will create a data analysis template that includes a neutral domain name that corresponds with each focus group question. Trained researchers will listen to the audio of each focus group session and create a summary of each domain, with space for other observations that may occur during data collection. Then, all text summaries will be collated into one matrix (focus group x domain) and assessed for similarities and differences across responses and by

domain. Matrices may also be set up by individual focus group or by respondent study arm (e.g., pooling all responses for those who participated in the intervention group), if appropriate. Matrices will be analyzed for gaps in the data, emergent themes and to generate summaries of responses from participants in each study arm.

Addition of a Usual Care Arm

To assess whether the experience of the participants within the trial differs from patients at UCM who did not participate in the trial during the study timeframe, we will include a Usual Care Arm based on the original eligibility criteria used to generate the ACRES recruitment lists of patients and include retrospective outcomes data (A1C and medications between 9-23-2020 to 9-16-2024).

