Among the 167 patients who were enrolled in attention control arm, 133 patients had an A1C result in EHR at 12 month follow up by May of 2024. These patients had an average reduction of 0.97% (SD 1.64%) in A1C from baseline to 12 month. Based on our literature review, we found no consistent pattern for A1C change in usual care arms in behavioral intervention trials published in 2023 and 2024.¹¹⁸⁻¹²⁹ Based on this finding, we assume no A1C change will be observed in our usual care arm. By a two-sample t-test, a sample size of 39 in the usual care arm would guarantee $\geq 90\%$ power to detect at least 0.97% difference in A1C with the common SD of 1.64% between the attention control arm and usual care arm with a two-sided significant level of 5%. To account for up to 20% of subject attrition at 12 months, the final total sample size of the usual care arm is 49.

For simplicity, we plan to conduct a 1:1 matching for the usual care arm vs attention control arm (i.e., 167 patients will be included in the usual care arm). The matching procedure involves three steps. First, we identify all the potential usual care arm patients using the original eligibility criteria and have CRI generate a deidentified (except month and year of dates) list of patients at UCM excluding those who were enrolled in the study and ages over 89. Second, we will only include patients who have an A1C $\geq 7.5\%$ within our trial recruitment time (09-23-2021 to 07-07-2023). Third, we use R MatchIt package to perform the matching. We use exact matching on A1C group (7.5-8, 8-8.5, 8.5-9.5, 9.5+) and the calendar quarter using month and year when the A1C test was conducted. This step ensures patients who are enrolled in the usual care arm have similar A1C values and baseline dates as the attention control arm. We will also use propensity score matching on other covariates, such as age, gender, race/ethnicity. After the matching, we test the balance of the data on these covariates.

J. Potential risks and benefits

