Given the shift to telehealth appointments at UCM and shelter-in-place orders due to the COVID-19 pandemic, we are planning to conduct this study completely remotely. We will also work with CRI to create an ACRES Report to obtain a list of eligible patients. Researchers will contact patients by phone and explain that patients may be eligible for a research study and screen patients for eligibility if the patient is interested. If the patient is eligible, researchers will send them an e-consent form using REDCap that is able to be filled out online or other methods described earlier. The e-consent process is one that has been developed successfully in our lab.

[name] and [name] lead the My Diabetes, My Community trial - a three-arm parallel pragmatic randomized controlled trial among older, predominantly African American patients with type 2 diabetes seen at the University of Chicago. A dementia diagnosis and inability to complete the study on their own are two of the exclusion criteria for the trial. During screening, it is possible for research assistants to contact patients living with dementia or their caregivers. When a patient with dementia and their caregiver are identified and screen out in the MDMC trial, there is an opportunity to ask whether they would be interested in participating in another trial they may be eligible for - the CommunityRx-Caregiver trial. The MDMC research assistant would ask if the patient is interested in hearing more about a trial they may be eligible for and whether it is ok to share their phone number with the CommunityRx-Caregiver team. In receiving verbal consent to share their phone number with the CommunityRx-Caregiver team, the MDMC research assistant will document this in the patients' screening data in REDCap and notify the MDMC Project Manager (PM). The MDMC PM will then flag this record to the CommunityRx-Caregiver PM. [name], who is also on the MDMC staff. A CommunityRx-Caregiver team member will then follow-up with the patient about participating in the CommunityRx-Caregiver study.

If we are able to safely approach patients in-person again, as we have done in prior trials in this setting, we will review the informed consent and study procedures with them.

In addition to recruiting via ACRES reports and CRI data mart, we will use the ITMs research profile website, <https://betheenewnormal.org/>, and researchmatch.org to post our study and to use it as a recruiting tool for eligible subjects.

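### The added usual-care arm has no step removing patients the trial's phone screen found ineligible, so such patients can be matched to attention-control participants

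*Combined protocol and SAP*

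**What the plan says.** Section I, under the usual-care heading, states the purpose: to see whether the experience of trial participants "differs from patients at UCM who did not participate in the trial during the study timeframe". The arm is to be "based on the original eligibility criteria used to generate the ACRES recruitment lists of patients". The first matching step uses slightly different words: "First, we identify all the potential usual care arm patients using the original eligibility criteria". The research informatics group (CRI) is to produce a de-identified "list of patients at UCM excluding those who were enrolled in the study and ages over 89". The second step keeps patients with an A1C of at least 7.5% in the recruitment window. The third matches exactly on A1C group and calendar quarter, and by propensity score on further covariates, of which age, gender and race/ethnicity are given as examples. Balance is then tested on those covariates.

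Section P describes recruitment. An ACRES report supplies a list, and researchers then phone the listed patients and check eligibility. It adds: "During screening, it is possible for research assistants to contact patients living with dementia or their caregivers". It names a dementia diagnosis and inability to complete the study unaided as exclusions, and describes patients with dementia being screened out.

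Section H gives the trial criteria. The age criterion is "Males and females 60 years of age or older", with no upper limit. The exclusions are inability to consent and complete assessments (dementia is specified), terminal illness, institutional residence, inability to use English or Spanish, and recent enrolment in either predecessor trial.

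**The concern.** Attention-control participants passed both the list and the phone screen. The usual-care patients are described as passing the list criteria only. If patients the trial would have refused sit in one arm and not the other, a difference in A1C change mixes the effect of taking part with the effect of whatever made those patients ineligible.

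The documents give a reason to expect such patients to differ. Section A reports guideline A1C goals that loosen from healthy to complex to very complex older patients. Section I lists health status among the confounders for the randomised analyses, but does not name it for the matching. The direction of any bias is unknown: treatment may be relaxed in such patients, or they may be tested less often.

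At stake is the reading of the comparison between attention control and usual care, which is sized on a 0.97-point difference.

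**Working it through.** **Step 1. Can a screen failure enter the usual-care pool?**
- Anyone drawn from the ACRES list and rejected by phone met the list criteria by construction. This holds whatever those criteria were.
- Reapplying the same criteria brings that person back. The two stated removals (enrolled, over 89) do not catch a screen failure aged 89 or below.
- The A1C filter removes only those without a value of at least 7.5% in the window.
- The named matching variables (A1C group, quarter, age, gender, race/ethnicity) do not measure capacity, terminal illness, residence or language. A balance test on those variables would not reveal the problem.
- On the broader wording of the first matching step, the answer is much the same. CRI is to "have CRI generate a deidentified (except month and year of dates) list", and such a list cannot show capacity to consent or ability to complete assessments as an interviewer could judge them.

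**Step 2. The plan's own sample size.** Inputs from section I: 133 attention-control patients with a 12-month A1C, difference 0.97, SD 1.64, two-sided 5%, power at least 90%, 20% attrition.
- SE with 39 usual-care patients = 1.64 × √(1/133 + 1/39) = 0.299.
- 0.97 / 0.299 = 3.25. By the normal approximation, power is 90.1% at n = 39. The noncentral t gives 89.8% at 39 and needs 40.
- 39 / 0.80 = 48.75, rounded up to 49.

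The stated 39 and 49 are reproduced.

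**Step 3. Precision as planned.** The plan matches 1:1 with 167 patients. Assume 133 of 167 (79.6%) have a 12-month A1C in each arm, as in attention control.
- SE = 1.64 × √(2/133) = 0.201.
- Power for 0.97 is 99.8%.

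Sample size is therefore not the limitation; comparability is.

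**Step 4. Possible size of the bias.** Let f be the ineligible share of the analysed usual-care patients, and d the difference in their mean A1C change. The contrast shifts by f × d. Neither f nor d is in the documents; both ranges are assumptions. The last two columns give the rejection rate at the 5% level when there is no true difference (noncentral t, 133 per arm, noncentrality f × d / 0.201).

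| f | Shift, d = 0.5 | Shift, d = 1.0 | Rejection, d = 0.5 | Rejection, d = 1.0 |
|---|---|---|---|---|
| 5% | 0.025 | 0.05 | 5.2% | 5.7% |
| 10% | 0.05 | 0.10 | 5.7% | 7.9% |
| 20% | 0.10 | 0.20 | 7.9% | 16.8% |
| 30% | 0.15 | 0.30 | 11.5% | 31.8% |

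The range runs from about one eighth of a standard error (0.025 / 0.201) to about 1.5 standard errors (0.30 / 0.201), or from 3% to 31% of 0.97.

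**The case against.** The strongest reply has five parts.

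- **The ACRES criteria are not listed.** Section C says candidates are pre-screened in the record, section P describes the report as listing eligible patients, and a dementia diagnosis is codable. The list may already exclude many such patients. This stands: the number affected cannot be known and may be small. It does not close the gap, because section P itself allows that the screen may reach people with dementia.
- **Section P names only dementia and inability to complete the study.** A reader might infer that terminal illness, institutional residence, language and phone or e-mail access were all checked only by phone. The documents do not say at which stage each was checked.
- **Selection continues after the list.** A reader might infer that every patient rejected by phone ends up in the arm. That is too strong: a qualifying A1C is needed, and only 167 are matched. The propensity covariates are given as examples, so others could be added. What stands is that no stated step or named variable deals with screen failures.
- **The stated comparison is with non-participants, and screen failures are non-participants.** The plan does not claim an eligible-but-not-enrolled group. That standard is inferred from its use of the trial's eligibility criteria, and the choice of target population is partly the investigators' to make.
- **The size is one assumption times another.** At d = 0.5 every shift is below one standard error. If ineligible patients are tested less often, the observed-data analysis will also contain fewer of them. Both points are fair; only the larger assumed pairs matter.

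**Conclusion.** The concern holds in a limited form. Followed as written, the plan can place patients already found ineligible for the trial in the usual-care arm, and nothing it names would remove or detect them. On the assumed ranges (f 5–30%, d 0.5–1.0 points) the contrast shifts by 0.025–0.30 points, against a standard error of about 0.20; the direction and the true share are unknown. The standard error follows the plan's own two-sample framework and assumes 133 evaluable patients per arm.

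The cut at age 89 is a minor mismatch. It sits in the de-identification sentence and reads as a privacy limit. No count is given, and the plan does not say whether attention-control participants over 89 leave this comparison. A reader might infer that it seriously distorts the arm; the documents do not support that.

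Nor do they support extending the point to the trial as a whole. The primary test is the randomised comparison of MDG with MDG+CRx, which is unaffected. This is an inexpensive improvement to an added, non-randomised comparison.

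**What to change.** List the ACRES criteria in the protocol. Then, before CRI de-identifies the list:

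1. Remove patients recorded as ineligible in the REDCap screening data, keeping those who declined and those never reached. Confirm IRB cover for this linkage, since these people did not consent to the trial.
2. Apply, at the index date, the section H exclusions that can be coded in the health record (dementia diagnosis, terminal illness, institutional residence, language), where the ACRES list did not already do so.
3. As a minor point, restrict attention-control patients in this comparison to age 89 or below, so that both arms share an age range.

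I would not filter on whether a phone number or e-mail address is on file, because that is not the access criterion in section H. Whether to require a type 2 diabetes diagnosis is a separate question.

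The cost is one linkage and filter alongside the exclusion of enrolled patients that CRI must already make, and a smaller candidate pool. Codes will miss some ineligible patients who were never screened. Volunteer bias remains and should be stated as a limitation.

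### Does the usual-care sample size fail because it treats the attention-control arm's own A1C fall (0.97) as the difference from usual care?

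*Combined protocol and SAP*

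**What the plan says.** All of this is in section I, Statistical analysis, under Addition of a Usual Care Arm.

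- **Source of the effect.** Of 167 attention-control patients, 133 had a 12-month A1C in the health record by May 2024. "These patients had an average reduction of 0.97% (SD 1.64%) in A1C from baseline to 12 month".
- **Assumption for usual care.** After reporting that recent trials showed no consistent usual-care trend, the plan says "we assume no A1C change will be observed in our usual care arm".
- **Power statement.** On a two-sample t-test at two-sided 5%, "a sample size of 39 in the usual care arm would guarantee" at least 90% "power to detect at least 0.97% difference in A1C with the common SD of 1.64". Allowing for 20% attrition, 39 becomes 49.
- **Size adopted.** The next paragraph says "we plan to conduct a 1:1 matching for the usual care arm vs attention control arm", giving 167 usual-care patients. They must have an A1C of at least 7.5% in the recruitment window. On matching it says: "We use exact matching on A1C group", together with calendar quarter of the test, and a propensity score for other covariates.

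No power or detectable difference is given for 167 against 167.

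**The concern.** A before-after change within one arm is not a difference between two arms. The two are equal only if the comparison group does not change at all. An inconsistent literature supports a range of values, not zero, and zero gives a larger difference than any usual-care fall would.

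The design itself gives reason to expect some fall. Usual-care patients are selected for a high A1C and matched within A1C bands, so regression to the mean should act on both groups. Section G also describes a declining local rate of poor control, from 29.2% to 26.6% between April 2019 and March 2020. That is a proportion over an earlier period, so it shows only that zero is not self-evident.

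The size justified (49) is also not the size used (167), so the power statement does not describe the planned comparison. If the premise failed badly and 39 evaluable patients were all there were, the comparison could be seriously underpowered while the text spoke of a guarantee. A reader might also take 0.97 as the expected benefit over usual care.

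**Working it through.** **Inputs, all from the section on the usual-care arm.** Difference 0.97; common SD 1.64; two-sided 5%; target power 90%; 133 attention-control patients with a 12-month value; attrition 20%; planned match 167 to 167.

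**1. Reproduce 39 and 49.** Hold attention control at 133.

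- Standard error = 1.64 × √(1/39 + 1/133) = 0.2986.
- 0.97 / 0.2986 = 3.248.
- Normal-approximation power = Φ(3.248 − 1.960) = 0.901, and 39 is the smallest usual-care number that reaches 90%.
- The non-central t gives 0.898 at 39 and needs 40, a difference of one patient.
- Attrition: 39 / (1 − 0.20) = 48.75, rounded up to 49.

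Both figures stand, given their inputs.

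**2. What the adopted size delivers.** With 20% loss, 167 × 0.8 = 133.6; take 133 per group.

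- Standard error = 1.64 × √(2/133) = 0.2011.
- Power for 0.97 (non-central t) = 0.998, against the 90% claimed.
- Detectable difference: 0.654 at 90% power and 0.565 at 80%.
- With no loss (167 to 167): 0.583 and 0.504.

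**3. Let usual care fall as well.** The difference becomes 0.97 minus the usual-care fall. The falls are my assumptions.

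| Assumed usual-care fall | Difference left | Power, 133 v 39 | Power, 133 v 133 |
|---|---|---|---|
| 0 | 0.97 | 0.898 | 0.998 |
| 0.2 | 0.77 | 0.727 | 0.968 |
| 0.3 | 0.67 | 0.607 | 0.913 |
| 0.4 | 0.57 | 0.475 | 0.806 |
| 0.5 | 0.47 | 0.347 | 0.644 |

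At 133 v 133, power is 0.905 for a fall of 0.31 and 0.896 for 0.32, so the 90% limit lies between them.

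**4. Usual-care patients needed for 90% power against 133.** A fall of 0.2 needs 76, or 76 / 0.8 = 95 with attrition. A fall of 0.3 needs 122, or 122 / 0.8 = 152.5, so 153. Both are within 167. A fall of 0.4 needs 256, or 256 / 0.8 = 320, which is beyond it.

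**5. Vary the number analysed.** The 133 is a count at May 2024, while recruitment ran to 7 July 2023 and outcome data run to 16 September 2024, so more attention-control values may arrive. With 167 v 133 the detectable difference is 0.62 (90%) and 0.54 (80%). In the other direction, suppose only complete pairs are kept and each side independently loses 20%: 167 × 0.8 × 0.8 = 106.9, about 107 pairs. Treated as unpaired, 107 v 107 gives 0.73 and 0.63, and power of 0.72 at a fall of 0.4. Even here the detectable difference is below 0.97.

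**The case for a change.** The strongest case for a change is that this is the only power figure in the documents, that it rests on a premise its own evidence does not establish, and that one sentence would repair it. The description is fair. The word guarantee promises more than a conditional calculation can, and the detectable difference for 167 to 167 is missing.

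The step from there to a needed change does not hold:

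- **The premise is disclosed.** The text says that zero change is assumed and labels 0.97 as a change from baseline to 12 months. Every power calculation is conditional on its planning values.
- **The documents do not show zero to be wrong.** An inconsistent pattern allows usual-care rises, which would increase power, as well as falls. Regression to the mean is a sound argument for some fall, but its size cannot be obtained from the documents.
- **The vulnerable number is not the one used.** The steep loss of power belongs to 39 evaluable patients, and the plan moves away from that size in the next paragraph.
- **Nothing operational depends on the figure.** The arm is built from retrospective records, so no recruitment or patient exposure turns on it. The plan will extract the actual usual-care A1C values, so the zero is a sizing input and does not enter the estimate.

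A rewrite would also bring conditions of its own. A statement for 133 per group presumes that all 167 find an exact match on A1C band and quarter, and that about a fifth lack a 12-month value. Step 5 of the working shows the figure moving either way if they do not. Calling the comparison exploratory would add a label that the section does not give this arm.

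**Conclusion.** No change to the plan is needed. The concern describes a disclosed planning assumption and an omitted detectable difference, not an arithmetic error: 39 and 49 are correct for the inputs given. The power statement should be read as conditional on no change in usual care, and 0.97 as attention control's own change, not as an estimate of benefit over usual care.

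The adopted match exceeds the justified 49 more than threefold (167 / 49 = 3.4) and is not shown to be underpowered. At 133 per group it has 99.8% power for 0.97. It detects about 0.65 with 90% power and 0.57 with 80%, and it tolerates an assumed usual-care fall of about 0.31 or 0.40 before dropping below those levels. Beyond about 0.40 power would be short, but the documents give no figure that places usual care there.

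These results assume SD 1.64 in both groups, an unpaired two-sided 5% t-test as in the plan, all 167 matched, and about 133 per group with a 12-month A1C. Matching may alter precision. Rewording would leave the number of patients, the matching, the analysis and the primary MDG versus MDG+CRx test as they are, so the result and conclusion would be the same. An analyst reporting this comparison can supply the detectable difference from the section's own inputs.
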